Strategies used for recruitment of individual participants (caregivers and residents), and procedures for delivery of the intervention, will be similar to those used in the feasibility study since they proved to be successful: resource groups, comprised of heads of wards and selected health personnel, will be established at each of the included nursing homes. Meetings will be scheduled to adapt delivery of the project to each individual institutions' resources and facilities, and members of the resource groups will be assigned the task of recruiting individual participants. Written informed consent will be requested for both residents and caregivers to be enrolled in the study. Nursing home residents constitutes a vulnerable group in which many individuals may have reduced decision-making capacity. For these individuals, deputy consent will be obtained from their next of kin. Residents receiving end-of-life palliative care are excluded. Both full- and parttime nursing staff will be included. Health personnel with purely administrative tasks (i.e., heads of institutions) are excluded. Following recruitment of participants and baseline measurements, nursing homes in the intervention group will be provided with SmartJournal toolboxes and packages with oral hygiene equipment, while nursing homes in the control group will receive oral hygiene equipment packages only. The SmartJournal toolboxes include tablets with SmartJournal installed, antibacterial touchscreen wipes, flashlights for monthly oral inspections, an instruction video, an instruction book and SmartJournal information posters. The oral hygiene equipment packages include toothbrushes for permanent teeth and prosthetic devices, dental floss, interdental brushes, toothpaste and inspection mirrors. Training, follow-up and technical support for SmartJournal users will be provided by project staff employed at the Oral Health Centre of Expertise Rogaland.

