3.3 Measurements

The effectiveness of SmartJournal in enhancing nursing home caregivers' capability, opportunity, motivation and routines related to oral care tasks will be measured by a survey questionnaire capturing components of the COM-B model [26]. Caregivers in both the intervention- and the control group will be asked to fill out the survey questionnaire three times: at baseline, 3 months and 9 months.

Effects of SmartJournal usage on nursing home residents' oral health will be assessed using the mucosal-plaque score (MPS) (21) as a primary outcome measure. MPS is comprised of a four-point plaque score (PS) and a four-point mucosal score (MS). PS = 1: no visible plaque, PS = 2: plaque is barely visible, PS = 3: moderate amount of plaque, PS = 4: large amount of plaque almost covering the whole surface of teeth. MS = 1: normal mucosa, MS = 2: mild inflammation, MS = 3: medium inflammation, MS = 4: strong inflammation. For both scores, if in doubt between 1 and 2, dental personnel are instructed to score 1. If in doubt between 3 and 4, they are instructed to score 4. The index is designed to evaluate oral health and oral hygiene in groups of individuals. This makes it a suitable index to be used when conditions

are not optimal to assess the patient's oral health. In a nursing home setting, dental personnel have limited equipment and poor light compared to an ordinary dental clinic setting. Therefore, using an index designed to be applied outside a dental clinic setting is feasible in this context. Residents in both the intervention- and the control group will have MPS assessment at three times: at baseline, 3 months and 9 months. MPS assessments will be performed by dental professionals employed at the Oral Health Center of Expertise Rogaland, Norway. Calibration will be undertaken to ensure reliability of the clinical measurements.

Effects of SmartJournal usage on documentation of oral health related issues in patient journals will be measured both quantitatively (i.e., frequency of documentation) and qualitatively (i.e., qualitative assessment of documentation) at three times throughout the project period: at baseline, 3 months and 9 months. Additional journal data shown to be associated with oral health will also be retrieved and used to describe the study sample and to be included as covariates in statistical analyses. These data include socio-demographics, medical conditions and prescribed medication.

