3.4 Power calculations and estimation of sample size for clinical outcomes

Experiences from the feasibility study show that resident participation may comprise a challenge due to high rates of morbidity, mortality and CRB in this part of the population. Estimation of sample size is largely reproduced from Overgaard et al. [32] who also used MPS as a primary outcome variable in their study on oral health in nursing home residents. Overgaard et al. based their power calculations on reductions in $MPS \geq 2$ from 60% to 15% as reported by Hede et al. [17]. Like Overgaard et al. we assume an alpha of 0.5, a power of 80% and a 33% drop-out rate due to the residents' frail condition and a median resident time of two years. Using the programme G*Power 3 [35] for power calculations, Overgaard et al. found that at least 92 residents should be included in each group for oral health assessments. A medical statistician has been consulted to further adapt the calculations to the present study setting (taking into account the number of eligible nursing homes and residents in the southern part of Rogaland), recommending the inclusion of 12 nursing homes each with 30 residents opted for oral health assessments. Thus, a total of 360 residents will be included for oral health assessments, 180 in the intervention and control group, respectively. All eligible caregivers in the 12 included nursing homes will be invited to take part in the survey capturing components of the COM-B model as described in the Measurements section (4.2). Experiences from the feasibility study indicate that this broad inclusion strategy, along with assigning the recruitment task to members of the institutions' resource groups, foster a sense of community regarding project participation. This may, in turn, motivate institutions and individual participants to remain part of the project throughout the study period.

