3.5 Data analyses

The statistical software package SPSS (IBM) will be used for analyses of quantitative data (i.e., survey data, MPS data and frequency data from patient journals). These analyses will include descriptive statistics (to describe the samples) and statistical techniques to look for changes and differences in the study variables within and between the intervention- and the control group throughout the project period - e.g., t-tests and analysis of variance (ANOVA)

tests. We hypothesize that SmartJournal usage will lead to favorable changes in variable scores. In caregivers: increased scores on the measured COM-B components (survey data). In residents: improved oral health as measured by MPS. In patient journals: increased reporting of oral health related issues. Additionally, regression analysis may be employed to investigate associations between study variables while adjusting for potential covariates (e.g., age, gender, educational level, medical conditions and prescribed medication). NVivo (Alfasoft) will be used as a tool in content analysis of oral health-related reports in patients journals. These analyses will (qualitatively) describe potential differences and changes in such reports within and between the intervention- and the control group throughout the project period.

4. Ethics and privacy

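### Section 3.5 names t-tests and ANOVA within and between groups for MPS and leaves adjustment optional; one between-group model adjusted for baseline MPS would usually, not always, be more precise

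*Protocol*

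**What the plan says.** Protocol section 3.5 covers the survey, MPS and journal-frequency data together. It plans to look for changes and differences "within and between the intervention- and the control group throughout the project period - e.g., t-tests and analysis of variance (ANOVA"). The hypothesis is equally general: "We hypothesize that SmartJournal usage will lead to favorable changes in variable scores". Adjustment follows as an extra: "Additionally, regression analysis may be employed to investigate associations between study variables while adjusting for potential covariates", with age, gender, education, medical conditions and medication as example covariates.

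Section 3.3 makes MPS the primary measure of residents' oral health and says that residents in both arms "will have MPS assessment at three times: at baseline, 3 months and 9 months". Section 3.2 places the baseline assessment before delivery of the tool: "Following recruitment of participants and baseline measurements, nursing homes in the intervention group will be provided with SmartJournal toolboxes". Section 3.4 gives the size: "the inclusion of 12 nursing homes each with 30 residents opted for oral health assessments", 180 residents per arm.

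Baseline MPS is thus planned for every resident and cannot have been affected by the tool, but neither section names it as a covariate. The lists are open examples, so it is not excluded either.

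**The concern.** Two features of 3.5 matter for the resident outcome.

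First, within-group and between-group comparisons stand side by side. A change inside the intervention arm mixes any effect of SmartJournal with everything else that moves MPS over the same months, including the hygiene packages given to both arms. Only the contrast between arms uses the randomisation. Without one named contrast, a within-arm improvement could be read as evidence of effect.

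Second, the named tests, in their plain form, do not adjust for baseline MPS. A comparison of changes subtracts the whole baseline value, which over-corrects when the correlation is moderate. A comparison of follow-up values ignores baseline and carries any chance imbalance between two sets of six homes. Baseline adjustment usually does better than both, and with 12 homes precision is scarce.

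**Working it through.** **Inputs from the protocol.** 12 homes of 30 residents, 180 per arm, so 180/30 = 6 homes per arm; MPS at baseline, 3 and 9 months; 33% drop-out. The protocol gives no baseline/follow-up correlation R and no intracluster correlation (ICC). Both are assumed here: R = 0.3, 0.5, 0.7 and ICC = 0.02, 0.05, 0.10. There is no plan figure for this point to reproduce. MPS is treated as a score.

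**Step 1: chance imbalance at baseline.** The SD of the arm difference, in score SDs, is sqrt(2 × (ICC/6 + (1 − ICC)/180)). This gives 0.132, 0.165 and 0.208 at ICC 0.02, 0.05 and 0.10.

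**Step 2: large-sample variance.** Take follow-up-only as 1. A change-score comparison has variance 2(1 − R) and a baseline-adjusted comparison 1 − R². Adjusted relative to change is (1 − R²)/(2(1 − R)) = (1 + R)/2.

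| R | Change score | Adjusted | Adjusted / change |
|---|---|---|---|
| 0.3 | 1.40 | 0.91 | 0.65 |
| 0.5 | 1.00 | 0.75 | 0.75 |
| 0.7 | 0.60 | 0.51 | 0.85 |

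Taking square roots, intervals are about 19%, 13% and 8% narrower than for change, and 5%, 13% and 29% narrower than for follow-up-only.

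**Step 3: cost with 12 homes if baseline enters as home means.** Estimating the slope multiplies the variance by about 1 + 1/(12 − 4) = 1.125, and one degree of freedom is lost: t(0.975) is 2.262 on 9 df against 2.228 on 10 df, a ratio of 1.015. Width relative to follow-up-only is sqrt((1 − R²) × 1.125) × 1.015:

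- R = 0.3: sqrt(1.024) × 1.015 = 1.03, or +3%
- R = 0.5: sqrt(0.844) × 1.015 = 0.93, or −7%
- R = 0.7: sqrt(0.574) × 1.015 = 0.77, or −23%

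Relative to change, sqrt((1 + R)/2 × 1.125) × 1.015 gives 0.87, 0.93 and 0.99, or −13%, −7% and −1%.

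**Step 4: baseline at resident level.** This costs less. In simulated trials of 12 homes × 30, with a random-intercept model and the same correlation at home and resident level, adjusted variance was 0.50 to 0.92 of follow-up-only and 0.64 to 0.85 of change, close to step 2.

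**Step 5: when the gain fails.** Suppose baseline and follow-up correlate within homes but home effects do not. The fitted slope then imports baseline home noise. With ICC 0.10 and within-home slope 0.7, the variance of a home mean at follow-up is 0.10 + 0.90/30 = 0.130. After adjustment it is 0.10 × (1 + 0.49) + 0.03 × (1 − 0.49) = 0.164, a ratio of 1.26. With ICC 0.02 the same sum gives 0.0465/0.0527 = 0.88. Simulation with home correlation 0 and resident correlation 0.3 to 0.7 gave 0.87 to 1.24 of follow-up-only and 0.57 to 0.78 of change.

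**Step 6: in detectable differences after drop-out.** With 30 × 0.67 = 20.1 residents per home and ICC 0.05, the design effect is 1 + 19.1 × 0.05 = 1.955. The standard error is sqrt(f × 1.955 × 2/120.6), with f from step 2. Multiplying by t(0.975) + t(0.80) (10 df unadjusted, 9 df adjusted) at R = 0.5 gives 0.559 SD for follow-up-only or change, and 0.491 SD adjusted. This counts the lost degree of freedom but not the cost of estimating the slope.

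**The case against.** The strongest reply is that this belongs to the statistical analysis plan, which is not at hand. The tests and covariates in 3.5 are marked as examples, and leaving a covariate out of an open list is no error. That stands as far as it goes: nothing here shows that the plan is wrong. But 3.5 does name techniques, within-group ones among them, and the proposal replaces those with a better one that uses data already planned.

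A second reply is that 3.5 speaks of changes over the project period, which points to change-score or repeated-measures analyses and not to a follow-up-only test. That is fair. The comparison with change scores is the more relevant one, and the larger gains against follow-up-only should not be presented as the expected benefit.

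A reader might infer more than the text supports:

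- *That 3.3 and 3.5 conflict on covariates.* Section 3.3 says that journal data are "to be included as covariates in statistical analyses. These data include socio-demographics, medical conditions and prescribed medication", while 3.5 uses a permissive verb for regression. These differ in firmness but can be read together, and neither concerns baseline MPS.
- *That the scale of MPS is contradictory.* The fall "from 60% to 15% as reported by" an earlier study is the basis of the power calculation borrowed in 3.4. No passage makes that dichotomy the outcome to be analysed.
- *That an unadjusted analysis would be biased or invalid.* Under randomisation, an unadjusted between-group test that accounts for nursing home is valid. How clustering is handled is a separate and weightier question, which baseline adjustment alone does not answer.

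**Conclusion.** The point holds as a modest improvement in precision and clarity, worth considering. Section 3.5 sets within-group tests beside between-group ones and ties no adjustment to the MPS contrast, although a baseline MPS is planned for each resident.

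If R lies between 0.3 and 0.7 at both home and resident level, adjustment removes about 15% to 35% of the variance of a change-score comparison and 9% to 49% of that of a follow-up-only comparison. If baseline is used only as home means, the gain is smaller, and at R = 0.3 there is none over follow-up-only. If home-level correlation is near zero, adjusting for resident baseline can be less precise than follow-up-only, though it still does better than change in the settings examined. All of this rests on assumed correlations and ICCs and on MPS analysed as a score. The case for one named between-group contrast does not depend on those assumptions.

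**What to change.** In 3.5, name the primary MPS analysis as one between-group comparison at one stated primary time point (3 or 9 months, for the sponsor to choose). Adjust it for each resident's own baseline MPS, with nursing home as a random effect and a small-sample degrees-of-freedom correction. If MPS is analysed as a score, this is a linear mixed model. Say that within-group changes are reported descriptively only.

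State a simple rule that keeps residents whose baseline MPS is missing, for example a single mean pooled over both arms plus a missing-baseline indicator. If such residents were excluded instead, each 5% missing would cost 360 × 0.05 = 18 of them. If a statistical analysis plan already fixes these items, a cross-reference in 3.5 is enough.

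The cost is wording in one section and no new data. The downside is one covariate, a rule to apply, and a gain in precision that is usual but not guaranteed.

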Collaborating partners from academic institutions: *[name]* is professor at Department of Clinical Dentistry, University of Bergen. [name] will assist in statistical analyses and supervise [name]'s PhD work together with [name] and [name]. *[name]* is professor and vice dean for education at the Faculty of health, University of Stavanger. [name] was involved in early phases of the SmartJournal project and will be engaged in future usage of SmartJournal components in health education. *[name]* is professor at the Faculty of health and sport sciences, University of Agder. [name] is experienced in intervention research and will assist in quality control of the intervention, analyses and dissemination.

Other collaborating partners include: NETTOP-UiS, Centre for development of institutional and home care services (USHT) in Rogaland and Norwegian Smart Care Cluster (NSCC). Additional research environments and collaborators may be included at a later stage if feasible.

8. Funding

The initial phases of the SmartJournal project (i.e., development of the prototype and the feasibility study) were funded by the Norwegian Regional Research Funds Vestland (RFF Vestland) and the Oral Health Centre of Expertise - Rogaland (TkRog) (project ID: 291051/2018). The research described in this protocol (i.e., the evaluation study) has recently received funding from the Norwegian Regional Research Funds Rogaland (RFF Rogaland, project ID: 332666/2022).

9. Time schedule

The study is scheduled between 01.02.2023 and 31.12.2025 (Table 1).

Table 1. Anticipated time schedule and research activities.

Activities	From	Quarter	To	Quarter
Recruitment and baseline measurements (T0)	2023	1	2023	2
Intervention*	2023	3	2023	4
Measurements at 3 months (T1)*	2023	4	2024	1
Measurements at 9 months (T2)*	2024	1	2024	3
Analyses and dissemination	2024	4	2025	4

*The intervention will last for 12 weeks. Since the start date may vary between included nursing homes, a 12 month period is scheduled to perform the intervention and measurements at T0, T1 and T2.

10. References

2. Kossioni A. The association of poor oral health parameters with malnutrition in older adults: a review considering the potential implications for cognitive impairment. *Nutrients*. 2018;10(11):1709.
